#### **4.7 Lost-to-Follow-up**

A participant will be considered lost to follow-up if they repeatedly fail to return for scheduled visits and is unable to be contacted by the study site.

The following actions must be taken if a participant fails to return for any required study visit:

- The site must attempt to contact the participant and reschedule the missed visit as soon as possible. If possible, the site should attempt to reschedule the missed visit within any allowed visit or treatment window.
  - The site should advise the participant that it is important to adhere to the assigned visit schedule.
  - The site shall attempt to ascertain whether or not the participant wishes to and/or should continue in the study.
- Prior to a participant being deemed lost-to-follow-up, the investigator or designee must make every effort to regain contact with the participant. All attempts to regain contact with the participant must be recorded in the participant's medical record.

If the participant continues to be unreachable, the participant will be considered to have withdrawn from the study.

#### **4.8 Study Completion**

Primary study completion is defined as the completion of the Week 24 visit, even if one or more interim visits or procedures was/were missed.

Completion of the Safety Follow-Up is defined by the completion of the Week 32 visit even if one or more interim visits or procedures was/were missed.

---

**5 ENROLLMENT AND STUDY PROCEDURES**

Table 2 presents the procedures and assessments at each of the scheduled visits. Details of each visit are provided in Section 5.1 through Section 5.6.

**Table 2 SCHEDULE OF PROCEDURES**

	Screening 										Treatment Period									
	-2	-1	1	2	3	4	5	6	N/A	7	8	9	10	11/ET	12	13/ET				
Visit Number	-2	-1	1	2	3	4	5	6	N/A	7	8	9	10	11/ET	12	13/ET				
Visit Day Window	-14	-7	1	8	22	29-35	43-49	57-63	78-84	85-91	113-119	141-147	155-161	162-168	190-196	218-224				
Visit Window		±2	±2	±2																
Visit Week	-2	-1	1	2	4	5	7	9		12	13	17	21	23	24/ET	28	32/ET			
ICF signed	X																			
Medical History/Update		X	X																	
Randomization			X																	
Study drug administered (post-assessments)				X		X		X		X		X		X						
Concomitant and Prior Medications					X	X	X	X		X		X		X		X				
Vital Signs 						X	X	X		X		X		X		X				
BMI							X				X		X		X					
Hematology 								X		X		X		X		X				
Lipids (fasting 8 hours) 								X		X		X		X		X				
Chemistry 									X	X	X	X	X	X	X	X				
Spot urine protein-creatinine ratio										X		X		X		X				
Urinalysis (including albumin) 											X		X		X					
Iron Indices 											X		X		X		X			
Serum Hepcidin												X		X		X				
TMPRSS6 Genotype test													X							
Infectious Disease Screen 														X		X				
Special RBCs 															X		X			
Screening (total) IL-6																				
IL-6 																				
hs-CRP 																				
Serum Pregnancy, FSH 																				
Zilitivekimab trough PK 																				
ADA 																				
12-lead ECG 																				
CKD Biomarkers 																				
NT-pro-BNP																				
Lp(a), ApoB, ApoA1 (fasting 8 hours) 																				

**Table 2 SCHEDULE OF PROCEDURES**

	Screening 										Treatment Period					Safety F/U 	
	-2	-1	1	2	3	4	5	6	N/A	7	8	9	10	11/ET	12	13/ET	
Visit Number	-2	-1	1	2	3	4	5	6	N/A	7	8	9	10	11/ET	12	13/ET	
Visit Day Window	-14	-7	1	8	22	29-35	43-49	57-63	78-84	85-91	113-119	141-147	155-161	162-168	190-196	218-224	
Visit Window		±2		±2													
Visit Week	-2	-1	1	2	4	5	7	9		13	17	21	23	24/ET	28	32/ET	
Lipid Profile by NMR spectroscopy (fasting 8 hours) 			X							X			X		X		
Cardiac Risk Biomarker 			X							X			X		X		
Storage samples for Exploratory Biomarkers and RNA Testing 			X							X			X		X		
DNA Testing (Stored Blood Samples)			X							X			X		X		
Limited Physical Examination 		X													X		
INR 		X	X	X	X	X	X	X		X	X	X	X		X		
Adverse Events		X	X	X	X	X	X	X		X	X	X	X		X		
PROMIS® 13a and Fatigue Items 			X							X			X		X		
PROMIS® Sexual Interest Items 			X							X			X		X		
CARES (Corvidia ePRO) 		X			X					X			X		X		
PGIS 		X			X					X			X		X		
PGIC 					X					X			X		X		
Optum SF-36 v2® 			X		X					X			X		X		
EQ-5D-5L 			X		X					X			X		X		

ET = Early Termination; F/U = Follow-up.

1. If a Screening laboratory (excluding hematology) result is outside inclusion criteria parameters screening may be extended up to one week to allow for retesting of lab test(s) that did not meet inclusion criteria.
2. Vital signs include temperature, respiratory rate, heart rate, and blood pressure (patients may be re-evaluated within 2 weeks, at the discretion of the PI if anti-hypertensive therapy has been started or increased as a result of initial screening blood pressure). Whenever possible, vital signs will be obtained after at least 5 minutes resting in the supine position or, when necessary, in a semi-recumbent position. Vital signs will be done prior to ECG recordings.
3. Hematology: hemoglobin, hematocrit, reticulocyte count, red blood count (RBC) indices (e.g., mean corpuscular volume (MCV), red cell distribution width (RDW), platelets, white blood count (WBC), WBC differential.
4. Lipids and subfractions (fasting 8 hours): total cholesterol, low density lipoprotein (LDL) cholesterol, high density lipoprotein (HDL), and triglycerides; Lp(a), ApoB, ApoA1.

5. Chemistry: sodium, potassium, chloride, bicarbonate (or CO2), calcium, phosphate, alanine aminotransferase (AST), blood urea nitrogen (BUN) creatinine, total bilirubin, direct bilirubin, alkaline phosphatase, albumin, glucose and eGFR calculated by CKD-EPI Creatinine Equation (<https://www.kidney.org/content/ckd-epi-creatinine-equation-2009>).
6. At Weeks 1 and 24, a portion of urine will be stored frozen for future analysis.
7. Iron Indices: TSAT, ferritin, iron, total iron binding capacity (TIBC).
8. Infectious Disease Screen: HIV 1 and 2, Hepatitis B surface antigen, Hepatitis C antibody, mycobacterium tuberculosis test (e.g., QuantiferON) is preferred, but a purified protein derivative (PPD) skin test read within 48-72 hours by a qualified healthcare professional can be performed. If the test comes back unable to perform analysis or indeterminate or confirmatory testing is required, the screening window is extended until central laboratory results are available. (<https://www.cdc.gov/tb/publications/factsheets/testing/skintesting.htm>).
9. Special RBC: reticulocyte hemoglobin content (CHr).
10. IL-6: Interleukin-6. Pre-dose sampling.
11. hs-CRP: high-sensitivity C-reactive protein. Test can be repeated once prior to randomization visit. Results after screening will be blinded after the first dose.
12. Pregnancy: β-hCG; FSH: Follicle Stimulating Hormone.
13. On dosing Weeks 1, 5, 9, 13, 17, and 21, trough PK samples to be collected within approximately -0.5 h pre-dose. Single PK blood samples will also be collected on Weeks 2, 4, 7, 23, 24/ET, 28, and 32/ET around the same time as the pre-dose samples were collected on previous dosing visits.
14. On dosing weeks 1, 5, 9, 13, 17, and 21, ADA: Anti-drug antibodies specimens to be collected within approximately 0.5 h pre-dose.
15. Standard 12-lead ECG will be recorded in the supine position (or with the patient as flat as possible) after vital signs assessments. The ECG will be locally read by the Investigator.
16. Chronic Kidney Disease (CKD) Biomarkers: cystatin C and UACR.
17. Cardiac Risk marker: SSA, fibrinogen and ST2.
18. Exploratory storage samples will be two 5-ml tubes of plasma, two 5-ml tubes of serum, and two 5-mL tubes of whole blood (PBMC testing at Screening, Week 13 and Week 24).
19. Limited physical exam to include skin, oropharynx, lungs, heart, abdomen, extremities (including feet), and any areas suggested by symptoms, with particular attention to signs of infection. May be performed by a physician-investigator or mid-level provider. Record abnormal findings in the source documents.
20. INR performed by a local laboratory on Warfarin patients only.
21. PROMIS ([Appendix B](#)), to be done on subjects' device at the clinic PRIOR to dosing.
22. CARES Corvidia ePRO ([Appendix D](#)), 7 day at home assessment on subject's personal device; the questionnaire will be answered daily for 7 days prior to dose (Screening Day -7 to Day -1 prior to Dose 1 (Visit 1), Dose 2 (Visit 4), Dose 4 (Visit 7), and the last 2 weeks after Dose 6 (Visit 23-24).

**CARES: Daily recall**

- (starts with Visit -1) = baseline average of the 7 consecutive assessments (Day -7 to Day -1) prior to Dose 1  
(starts with Visit 3) = end of month of Dose 1  
(no visit) = end of month of Dose 3  
(starts with Visit 10 and Visit 11) = starts 2 weeks after Dose 6
23. PGIS ([Appendix E](#)), to be done on subjects' device on the last day of CARES assessment.
  24. PGIC ([Appendix E](#)), to be done on subjects' device at the clinic PRIOR to dosing.
  25. Optum SF-36 v2® Health Survey ([Appendix C](#)), to be done on subjects' device at the clinic PRIOR to dosing.
  26. EQ-5D-5L ([Appendix F](#)), to be done on subjects' device at the clinic PRIOR to dosing.

After signing the ICF, patients should be registered into the electronic data capture system to obtain a patient identification number for the study.

### **5.1                   Screening Visit Procedures (Up to 2 weeks, Days -14 to -7) – Initial Screening**

Screening will be conducted in a stepwise manner. If a Screening laboratory result is outside inclusion criteria parameters screening may be extended up to one week to allow for retesting of lab test(s) that did not meet inclusion criteria.

Prior to conducting any study procedures informed consent will be obtained from the patient by the investigator (or other study staff who are conducting the informed consent interview). The Initial Screening procedures will be conducted after informed consent has been obtained. The following will be performed according to [Table 2](#).

- ICF signed
- Hematology
- Chemistry
- Iron Indices
- TMPRSS6 Genotype
- hs-CRP (may be repeated once up to randomization)
- Screening IL-6 (total)

### **5.2                   Screening Visit Procedures (Week -1; Days -7 to -1) – Full Screening**

Every effort should be made to obtain the blood tests for each visit on the same day of the week (e.g. on Wednesdays).

The following list summarizes the procedures for Week -1. Please see [Table 2](#) for full details.

- Medical History
- Concomitant and Prior Medications
- Vital Signs
- Hematology
- Lipids (fasting 8 hours)
- Chemistry

- Spot urine protein-creatinine ratio
- Infectious Disease Screen (If the test comes back unable to perform analysis or indeterminate or confirmatory testing is required, the screening window is extended until central laboratory results are available)
- Serum Pregnancy, FSH
- 12-lead ECG
- CKD Biomarkers
- NT-pro-BNP
- Lp(a), ApoB, ApoA1 (fasting 8 hours)
- Storage samples for Exploratory Biomarkers and RNA Testing (PBMC testing)
- DNA Testing – Stored Blood Samples
- Limited Physical Examination
- CARES Corvidia ePRO
- PGIS

The following sections summarize the procedures for the Treatment Period. Please see [Table 2](#) for full details.

### **5.3 Treatment Period (Study Weeks 1 - 21)**

**Important:** Study Visits during which Study Drug injections are required should be planned for the same day of the week so that Study Drug administration can occur on a schedule of every 28 days. See [Section 6.1.1](#) for guidance on missed doses.

#### **5.3.1 Visit 1, Week 1, Day 1 (Pre-Dose)**

- Medical History (update if necessary)
- Randomization (may occur on Day -1 if needed)
- Concomitant and Prior Medications
- Vital Signs
- BMI
- Hematology
- Lipids (fasting 8 hours)

- Chemistry
- Urinalysis (including albumin); portion stored frozen
- Iron indices
- Serum hepcidin
- Special RBCs
- IL-6 (pre-dose)
- hs-CRP
- Ziltivekimab trough PK
- ADA (pre-dose)
- CKD Biomarkers
- NT-pro-BNP
- Lp(a), ApoB, ApoA1 (fasting 8 hours)
- Lipid profile by NMR spectroscopy (fasting 8 hours)
- Cardiac Biomarkers: SSA, fibrinogen and ST2
- Coagulation (INR): Patients on warfarin only
- Adverse Events
- PROMIS® 13a and Fatigue Items
- PROMIS® Sexual Interest Items
- Optum SF-36 v2® Health Survey
- EQ-5D-5L

### **5.3.2           Visit 1, Week 1, Day 1 (Dosing/Post-Dose)**

Administration of the first dose of Study Drug will continue to define Study Day 1. Prepare the Study Drug prior to the anticipated time of administration (see [Section 6.1.1](#) and Pharmacy Manual).

- Study Drug (after all assessments)

**5.3.3                   *Visit 2, Week 2, Day 8***

- Concomitant and Prior Medications
- Hematology
- Chemistry
- Ziltivekimab trough PK
- ADA
- Coagulation (INR): Patients on warfarin only
- Adverse Events

**5.3.4                   *Visit 3, Week 4, Day 22***

- Concomitant and Prior Medications
- Vital Signs
- Hematology
- Chemistry
- IL-6
- hs-CRP
- Ziltivekimab trough PK
- ADA (pre-dose)
- Coagulation (INR): Patients on warfarin only
- Adverse Events
- CARES Corvidia ePRO
- PGIS

**5.3.5                   *Visit 4, Week 5***

- Study drug administered (after all assessments)
- Concomitant and Prior Medications
- Vital Signs

- Hematology
- Chemistry
- IL-6 (pre-dose)
- hs-CRP
- Ziltivekimab trough PK
- ADA (pre-dose)
- Coagulation (INR): Patients on warfarin only
- Adverse events
- PROMIS® 13a and Fatigue Items
- PROMIS® Sexual Interest Items
- PGIC
- Optum SF-36 v2® Health Survey
- EQ-5D-5L

#### **5.3.6                   *Visit 5, Week 7***

- Concomitant and Prior Medications
- Hematology
- Chemistry
- Ziltivekimab trough PK
- ADA
- Coagulation (INR): Patients on warfarin only
- Adverse Events

#### **5.3.7                   *Visits 6 through 9, Weeks 9 through 21***

- Concomitant and Prior Medications (not Week 12)
- Vital Signs (not Week 12)
- BMI (Week 13 only)

- Hematology (not Week 12)
- Lipids (fasting 8 hours; Week 13 only)
- Chemistry (not Week 12)
- Spot urine protein-creatinine ratio (Week 13 only)
- Urinalysis (including albumin) (Week 13 only)
- Iron Indices (Week 13 only)
- Serum hepcidin (Week 13 only)
- Special RBCs (Week 13 only)
- IL-6 (pre-dose) (not Week 12)
- hs-CRP (not Week 12)
- Ziltivekimab trough PK (not Week 12)
- ADA (pre-dose) (not Week 12)
- CKD Biomarkers (Week 13 only)
- NT-pro-BNP (Week 13 only)
- Lp(a), ApoB, ApoA1 (fasting 8 hours; Weeks 9 and 13 only)
- Lipid profile by NMR spectroscopy (fasting 8 hours; Week 13 only)
- Cardiac Risk Biomarkers: SSA, fibrinogen and ST2 (Week 13 only)
- Storage samples for Exploratory Biomarkers and RNA Testing (Week 13 only)
- Coagulation (INR): Patients on warfarin only (not Week 12)
- Adverse Events (not Week 12)
- PROMIS® 13a and Fatigue Items (Week 13 only)
- PROMIS® Sexual Interest Items (Week 13 only)
- CARES Corvidia ePRO (Week 12 only)
- PGIS (Week 12 only)
- PGIC (Week 13 only)
- EQ-5D-5L (Week 13 only)
- Optum SF-36 v2 (Week 13 only)

**5.3.8                   Visits 6 through 9, Weeks 9 through Week 21 (Dosing/Post-Dose)**

- Study Drug (after all assessments) (not Week 12)

**5.3.9                   Visit 10, Week 23 and Visit 11, Week 24/ET**

- Concomitant and Prior Medications
- Vital Signs
- BMI (Week 24 only)
- Hematology
- Lipids (fasting 8 hours)
- Chemistry
- Urinalysis (including albumin); portion stored frozen at Week 24 only
- Iron Indices
- Serum hepcidin (Week 24 only)
- Special RBCs (Week 24 only)
- IL-6
- hs-CRP
- Ziltivekimab trough PK
- ADA
- 12-lead ECG (Week 24 only)
- CKD Biomarkers
- NT-pro-BNP
- Lp(a), ApoB, ApoA1 (fasting 8 hours)
- Lipid profile by NMR spectroscopy (fasting 8 hours)
- Cardiac Biomarker: SSA, fibrinogen and ST2 (Week 24 only)
- Storage samples for Exploratory Biomarkers and RNA Testing (Week 24 only)
- Limited Physical Examination (Week 24 only)

- Coagulation (INR): Patients on warfarin only
- Adverse Events
- PROMIS® 13a and Fatigue Items
- PROMIS® Sexual Interest Items (Week 24 only)
- CARES (Corvidia ePRO) [2 weeks after Week 21 (Dose 6) for 14 consecutive days]
- PGIS (Week 24 only)
- PGIC (Week 24 only)
- Optum SF-36 v2®
- EQ-5D-5L (Week 24 only)

#### **5.4 Safety Follow-Up Visits 12 and 13 Procedures (Study Weeks 28 and 32)**

- Concomitant and Prior Medications
- Vital Signs
- Hematology
- Lipids (fasting 8 hours)
- Chemistry
- Iron Indices
- Special RBCs
- IL-6
- hs-CRP
- Ziltivekimab trough PK
- ADA
- Adverse Events

#### **5.5 Unscheduled Visit**

Additional clinical visits may be scheduled at the Investigators' discretion in order to follow or evaluate AEs. The reason for a given unscheduled visit will be recorded.

The following must be performed at any unscheduled visit occurring prior to Week 32:

- Record adverse events
- Record any medication changes.

## 5.6 Early Termination Visit

There are two possible types of Early Termination visits:

**Early Termination Visit 1 (ET-1):** Randomized patients terminating from the study prematurely prior to Study Week 24 should undergo an Early Termination Visit during which Week 24 procedures are performed.

**Early Termination Visit 2 (ET-2):** Randomized patients terminating from the study prematurely after Study Week 24 visit, but before Week 32 should undergo an early termination visit during which Week 32 procedures are performed.

Criteria for discontinuation of Study Drug can be found in [Section 4.3](#).

Patients may be withdrawn from the study for a number of reasons, including those outlined below:

- Patients withdrawing their consent for all study procedures. Patients must be given the option to continue to give consent for passive follow-up (i.e. by means of chart review) for adverse events through Study Week 21.
- Discontinuation of the study by the Sponsor.

## **6 DRUG SUPPLIES AND DOSING**

### ***6.1.1 Dosing and Administration***

The dose of Ziltivekimab for subcutaneous (SC) injection must be prepared using aseptic techniques. Drug Product is presented as a single use vial and any unused portion must be discarded.

Ziltivekimab is supplied as a liquid for injection.

The rationale for the planned doses in the study is described in [Section 3.5.4](#). Details on the dosing and administration are provided in [Table 3](#), and the composition for Ziltivekimab for injection and amount per mL are provided in [Table 4](#).

Personnel responsible for study drug preparation should have an appropriate background (i.e., physician, pharmacist, pharmacy technician, nurse, or other personnel approved by the Sponsor) and has been appropriately trained. Please see Pharmacy Manual for full details. The final required volume of Ziltivekimab is provided in [Table 3](#).

Please see the Pharmacy Manual for instructions on preparing and administering the Study Drug and storage of prepared Study Drug.

#### Special Situations

Patients who miss a dose of Study Drug may receive the missed Study Drug up to 15 days later.

If the missed dose cannot be administered within this time frame, the dose should be considered “missed” and the next dose administered at the next study visit as planned.

In the above special situations, please ensure that blood testing and PK sampling that is timed with the administered dose must be adhered to.

**Table 3** Planned Ziltivekimab Doses and Administered Volumes

	Dose Cohort 1	Dose Cohort 2	Dose Cohort 3	Dose Cohort 4
Intervention Name	Ziltivekimab	Ziltivekimab	Ziltivekimab	PBO
Type	Active Drug	Active Drug	Active Drug	Comparator
Dose	7.5 mg	15 mg	30 mg	N/A
Dose Administration	7.5 mg in 1 mL injection	15 mg in 1 mL injection	30 mg in 1 mL injection	1 mL PBO injections\
Route of Administration	SC injections	SC injections	SC injections	SC injections
Frequency	Every 28 days per SOA	Every 28 days per SOA	Every 28 days per SOA	Every 28 days per SOA

Abbreviations: PBO = placebo; SC = subcutaneous; SOA = schedule of activities

The date and time of administration of Study Drug must be recorded in the appropriate sections of the CRFs.

#### **6.1.2 Storage**

Ziltivekimab and placebo must be stored at 2 to 8 °C in the original container and must not be frozen.

#### **6.1.3 Formulation and Packaging**

**Table 4** Composition for Ziltivekimab for Injection, Amount per mL (7.5 mg/Vial, 15 mg/Vial, 30 mg/Vial, and Placebo)

Component	Amount per mL (7.5 mg vial)	Amount per mL (15 mg vial)	Amount per mL (30 mg vial)	Amount per mL (Placebo vial)
Ziltivekimab	7.5 mg	15 mg	30 mg	0 mg
Trehalose dihydrate	50.00 mg	50.00 mg	50.00 mg	50.00 mg
L-Arginine monohydrochloride	14.75 mg	14.75 mg	14.75 mg	14.75 mg
L-Methionine	1.49 mg	1.49 mg	1.49 mg	1.49 mg
L-Histidine	1.55 mg	1.55 mg	1.55 mg	1.55 mg
L-Histidine mono-hydrochloride monohydrate	2.10 mg	2.10 mg	2.10 mg	2.10 mg
Polysorbate 80	0.70 mg	0.70 mg	0.70 mg	0.70 mg
Water for Injection	q.s. to 1.0 mL	q.s. to 1.0 mL	q.s. to 1.0 mL	q.s. to 1.0 mL

Abbreviations: q.s. = quantum satis

## **6.2 Drug Accountability and Compliance**

The dispensing pharmacist or designated qualified individual will write the date dispensed, dose dispensed, and the patient's identification number, and initials on the Drug Accountability Source Documents. All medication supplied will be accounted for on the Drug Accountability Record. All partially used or unused drug supplies will be destroyed at the site in accordance with approved written site procedures or returned to Corvidia Therapeutics. The Investigator will maintain a record of the amount and dates when unused supplies were either destroyed or returned to Corvidia Therapeutics. All records will be retained as noted in [Section 13.5](#).

## 7 PRIOR AND CONCOMITANT MEDICATIONS AND TREATMENTS

### 7.1 Prior Medications and Treatments

See [Section 4.1](#) and [Section 4.2](#) for restrictions on prior medications and treatments.

### 7.2 Concomitant Medications and Treatments

Patients with cardiovascular disease should be treated according to published guidelines throughout the trial; in addition, patients may receive concomitant medications as clinically indicated with the following restrictions:

Systemic immunosuppressive drugs (i.e., such as cyclosporine, tacrolimus, sirolimus, mycophenolate, oral and intravenous glucocorticoids other than prednisone [or equivalent] up to a dose of 5 mg per day) may not be prescribed at any time during Study. Topical use (e.g., cyclosporine eye drops) is not restricted

*Note: Use of otic, ophthalmic, inhaled, and topical corticosteroids or local corticosteroid injections are not restricted. Short-term systemic glucocorticoid use (e.g., less than 5 consecutive days) for managing acute illnesses is also not restricted.*

Narrow therapeutic window medications that are influenced by CYP enzymatic pathways (See list in [Appendix A](#)) may not be prescribed at any time during Study.

- Warfarin is permitted, but the INR must be monitored closely and, at minimum, according to the protocol Schedule of Events (see [Table 2](#)).

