### **3.4 Duration of the Study**

The study will consist of three periods: Screening, Treatment Period, and Safety Follow-Up Period. The total study duration for an individual patient will be approximately 8-9 months. The study period durations are as follows:

Screening Period: up to 2 weeks [Days -14 to -1]

- Starts with the first date that Initial Screening procedures were performed. The first procedure also defines the initial screening visit date

Treatment Assessment Period: 24 weeks [Week 1, Day 1 through Week 24, ]

- Starts with the first administration of study drug/randomization (Day 1)

Safety Follow-Up Period: 8 weeks [Weeks 25 through 32]

- Safety period starts 4-weeks after last treatment dose 6.

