#### ***3.5.2 Rationale for Dosing and Length of Safety Evaluation***

Inhibition of free IL-6 greater than 90% is needed to achieve biologic effect, because growth factors and soluble cytokines in general are able to elicit signaling with receptor occupancies of less than 10%. A basic logarithmic dose escalation scheme was used after modeling of

IL-6 binding and the PK-PD (hs-CRP) relationship from the concluded Phase 1 trial in RA patients (Study D4430C00001). Based on the clearance of Ziltivekimab (dictated by the “YTE” Fc mutation), the duration of safety monitoring and follow-up for PK, IL-6, and antibody testing to 32 weeks is planned.

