### 3.5.4.1 Pharmacokinetic modeling

To date, the Ziltivekimab clinical program is comprised of 2 studies, both of which are placebo-controlled ascending dose studies. In the first of these studies (Study COR-001-01), patients with ESRD were administered intravenous (IV) infusions of study drug every 2 weeks for a total of 6 doses. Ten patients per cohort were randomized in a 1:4 ratio to placebo or Ziltivekimab (2, 6, and 20 mg).

In the second study (Study COR-001-SC1), patients with CKD were administered single subcutaneous (SC) doses of study drug. Four patients per cohort were randomized in a 1:3 ratio to placebo or Ziltivekimab (5, 15, and 50 mg).

The PK parameters are generally consistent with those expected for a monoclonal antibody. Absolute bioavailability (F) of SC administered Ziltivekimab is 69%, and the mean time of occurrence for peak serum Ziltivekimab concentrations ( $t_{max}$ ) after SC dosing ranged from 8 to 15 days, with an absorption half-life of 3 days. Terminal elimination half-lives ( $t_{1/2,z}$ ) differed between the ESRD patients (mean  $t_{1/2,z}$  ranging from 38 to 44 days) and CKD patients (mean  $t_{1/2,z}$  ranging from 48 to 56 days). While these results suggest that the rate of Ziltivekimab elimination may increase with decreasing renal function, a prior observation in rheumatoid arthritis patients that Ziltivekimab clearance is much slower than the glomerular filtration rate implies that the apparent elimination rate difference is not due to renal function *per se*, but more likely other physiological changes that accompany decreased renal function.

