### **Prior or Current Medications**

21. Received any investigational drug within 30-days prior to screening visit.
22. Received a live vaccine product within 14 days of study drug administration (Day 1) or expect to receive live vaccine during the Treatment Period (receiving a live vaccine within 14 days prior to enrollment is allowed).
23. Treatment with a hypoxia-inducible factor (HIF) stabilizer (e.g., molidustat, roxadustat) or an erythropoietin-mimetic, e.g., erythropoietin alpha or beta, darbopoietin alpha, or continuous erythropoiesis receptor activator (CERA), within 6-weeks prior to randomization or during treatment period.
24. Expected to receive any investigational drug or any of the exclusionary drugs listed in Section 15.1 during the Treatment Period or Safety Follow-Up Period.
25. Chronic use of systemic immunosuppressive drugs during the screening period or anticipated use of such drugs any time during the study. Note: Use of otic, ophthalmic, inhaled, and topical corticosteroids or local corticosteroid injections are not exclusionary. Oral prednisone up to 5 mg per day is (or equivalent) is permitted if dose has been stable for at least 4 weeks prior to screening, and no dose changes are planned during study participation.
26. Use of systemic antibiotics, systemic antivirals, or systemic antifungals during the screening period (“Systemic” is defined as oral or intravenous drugs that are absorbed into the circulation).
27. Requiring an indwelling catheter of any type.

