#### **4.6 Participant Discontinuation/Withdrawal from the Study**

The following are descriptions of participant discontinuation and withdrawal from the study. This is not an exhaustive list, and each instance should be evaluated on a case-by-case basis.

- Withdrawal of consent. A participant may elect to withdraw consent to treatment at any time.
- Participants withdrawing their consent for all study procedures must be given the option to continue to give consent for passive follow-up (i.e., by means of chart review) for AEs.
- Participants discontinuing study drug treatment after receiving any amount of study drug should undergo all early termination and safety follow-up study procedures per the SOA ([Section 5.3.9](#) and [Section 5.6](#)) unless the participant also explicitly withdraws consent for these procedures as mentioned above. The study drug has a long pharmacodynamic effect. Therefore, continued monitoring for pharmacodynamic effects and safety is prudent.

- A participant may be withdrawn at any time at the discretion of the investigator for safety, behavioral, compliance, or administrative reasons. Participation in the early termination and safety follow-up procedures will be evaluated on a case-by-case basis. If possible, participants should take part in the early termination and safety follow-up procedures in the SOA ([Section 5.3.9](#) and [Section 5.6](#)).
- If the participant withdraws consent for disclosure of future information, the sponsor may retain and continue to use any data collected before such a withdrawal of consent.
- If a participant withdraws from the study, the participant may request destruction of any samples taken and not tested. The investigator must document this in the site study records.

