## **15 APPENDICES**

### **15.1 Appendix A Exclusionary Drugs**

The following medications are metabolized by CYP450 enzymatic pathways and have a narrow therapeutic window. The use of these medications from one day prior to Randomization (Day -1) through Study Week 24 is prohibited.

digoxin

theophylline

terfenadine

tizanidine

quinidine

phenytoin and its derivatives

taxane chemotherapeutic agents

cyclosporine

mTOR inhibitors (e.g., sirolimus, tacrolimus)

ergot alkaloids

antipsychotic medications (specifically pimozide, thioridazine)

fentanyl and derivatives (e.g., alfentanil and sufentanil)

---

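### Appendix A ends its drug prohibition at Week 24, whereas Section 7.2 and exclusion 24 carry the same list through Safety Follow-Up to Week 32

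*Protocol*

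**What the plan says.** Four places in the Protocol bear on how long these drugs are banned.

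- **Section 7.2** restricts "Narrow therapeutic window medications that are influenced by CYP enzymatic pathways", refers to Appendix A for the list, and says that they "may not be prescribed at any time during Study". It gives no calendar end date.
- **Section 3.4** fixes what the study comprises: "The study will consist of three periods: Screening, Treatment Period, and Safety Follow-Up Period". It puts Safety Follow-Up at Weeks 25 through 32.
- **Exclusion 24** (Section 4.2, Prior or Current Medications) excludes patients expected to receive any "exclusionary drugs listed in Section 15.1 during the Treatment Period or Safety Follow-Up Period".
- **Appendix A** (Section 15.1), which holds the list, says: "The use of these medications from one day prior to Randomization (Day -1) through Study Week 24 is prohibited".

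Two further statements bear on how long study drug persists. Section 3.5.2 says that, based on the drug's clearance, "the duration of safety monitoring and follow-up for PK, IL-6, and antibody testing to 32 weeks is planned". Section 4.6 says: "The study drug has a long pharmacodynamic effect".

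**The concern.** Section 7.2 and Appendix A state the same rule for the same drugs with different end dates, and no other section reconciles them. The appendix is the page a prescriber would check, because only there are digoxin, theophylline, quinidine, phenytoin, fentanyl and the others named. An explicit end date on that page reads as release after Week 24.

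Two things are at stake, both in the conduct of follow-up. A narrow-therapeutic-window drug could be started in Weeks 25 to 32 while study drug is still in the circulation. And it would be unclear whether such a start is a protocol deviation, although the visits at Weeks 28 and 32 still collect concomitant medications, drug levels and adverse events (Section 5.4).

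**Working it through.** **Step 1. The two windows.**

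| Source | Start | End |
|---|---|---|
| Section 7.2, read with 3.4 | any time in the study, so including Screening | end of Safety Follow-Up, Week 32 |
| Exclusion 24 (eligibility; expected use) | Treatment Period | Safety Follow-Up, Week 32 |
| Appendix A | Day -1 | Week 24 |

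Gap at the end: 32 - 24 = 8 weeks, or 8 x 7 = 56 days (Days 169 to 224). The start dates also differ: Section 7.2 covers Screening and Appendix A begins at Day -1.

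**Step 2. Could the study in Section 7.2 mean Week 24?** Section 4.8 ties primary study completion to the Week 24 visit. The same section defines completion of Safety Follow-Up separately at Week 32, Section 3.4 lists follow-up as a study period, and exclusion 24 names that period for this very list. The Week 24 reading does not fit, and Appendix A is the outlier.

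**Step 3. Is study drug still present in Weeks 25 to 32?** The Protocol gives no prediction for these weeks, so this is derived.

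Inputs:
- terminal half-life in CKD patients "ranging from 48 to 56 days", and 38 to 44 days in ESRD patients (Section 3.5.4.1)
- absorption half-life 3 days (Section 3.5.4.1)
- six doses every 28 days, placed on Days 1, 29, 57, 85, 113 and 141 (Section 3.1)
- predicted median Dose 6 troughs of 723, 1446 and 2892 ng/mL (Section 3.5.4.3)

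The absolute troughs cannot be reproduced, because volume and clearance are not given. Their ratios are 1446/723 = 2 and 2892/723 = 4. These match the dose ratios, so linear scaling is consistent with the Protocol.

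Model (an assumption of this check): one compartment with first-order absorption. Each dose contributes

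c(t) = ka/(ka - ke) x [exp(-ke t) - exp(-ka t)], with ka = ln 2/3 = 0.231 per day and ke = ln 2/half-life,

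and the six contributions are summed. The Dose 6 trough is taken at Day 169, 28 days after Dose 6.

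| Half-life | Summed level, Day 169 | Summed level, Day 224 | Day 224 / Day 169 |
|---|---|---|---|
| 48 d (CKD) | 1.950 | 0.882 | 0.45 |
| 56 d (CKD) | 2.230 | 1.130 | 0.51 |
| 38 d (ESRD) | 1.551 | 0.569 | 0.37 |
| 44 d (ESRD) | 1.797 | 0.756 | 0.42 |

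Hand check: absorption is almost complete by Day 169, so the ratio is close to exp(-55 ke), with 55 = 224 - 169. That gives 0.452 at 48 days and 0.506 at 56 days.

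Scaled to the stated troughs with the CKD half-lives, the Day 224 levels are about 327 to 366 ng/mL (7.5 mg), 654 to 733 ng/mL (15 mg) and 1308 to 1465 ng/mL (30 mg).

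**The case against.** **Both rules can be obeyed.** Appendix A does not say that the drugs are allowed after Week 24, and a site that follows Section 7.2 satisfies both texts. Sites reach the list through Section 7.2 or exclusion 24, which both carry the longer window. Patients expected to need these drugs in follow-up are already excluded. Cyclosporine, sirolimus and tacrolimus are also caught by the separate immunosuppressant sentence in Section 7.2. All of this is correct and limits the practical reach. It does not remove the conflict, because a stated end date on the only list implies release and leaves deviation status unclear.

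**The pharmacokinetic model is thin.** The 48 to 56 days come from a study that enrolled eGFR 20 to 60 (Section 1.4.2), whereas this trial enrols down to eGFR just above 10, and Section 3.5.4.1 allows that elimination may be faster with worse renal function. Section 1.4.3 reports a biphasic decline after IV dosing. The Dose 6 trough might also mean the pre-dose sample on Day 141, which would make the Day 224 level at 7.5 mg about 344 to 389 ng/mL. These points stand, and they are why the ESRD range is shown. None of them alters the finding that an appreciable fraction of drug remains.

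**Sections 3.5.2 and 4.6 concern monitoring, not CYP substrates.** That is also right. They show that the drug persists; they do not set a washout for the ban.

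**A stronger reading that the Protocol does not support.** With half-lives of 48 to 56 days, the Day 224 level is 1.24 to 1.52 times the trough after the first dose. A reader might infer that the ban is lifted at a level the Protocol itself treats as unsafe. That does not follow. The ban begins on Day -1, before any exposure, so the first-dose trough is not an interaction threshold. The ratio is also sensitive to the half-life: 1.10 at 44 days and 0.88 at 38 days.

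**Conclusion.** The inconsistency is real and rests on the text alone: one ban, two end dates 8 weeks apart, and different start dates as well. Under the one-compartment assumption, about 45 to 51% of the Dose 6 trough remains at the end of Week 32 with the CKD half-lives, or about 37 to 42% with the ESRD half-lives. Ending the ban at Week 24 therefore cannot be explained by the drug having cleared.

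The conclusion stops there. The Protocol states no interaction size, no threshold concentration and no rate of use of the listed drugs, so no exposure cut-off and no number of patients harmed is claimed. The Week 13 hs-CRP endpoint falls inside the window that both texts cover and is unaffected, as are the sample size and the error rate. This is a minor correction to a safety-conduct rule.

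**What to change.** In Appendix A, replace the Week 24 end date with the last safety follow-up visit (Week 32). State one start date in both places, for example by having the sentence on these drugs in Section 7.2 run from Day -1 through Week 32. Changing the end date alone would leave the start dates in conflict. The immunosuppressant sentence in Section 7.2 and exclusion 25 can stay as they are.

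The cost is a slightly longer explicit restriction on prescribing during follow-up for sites that had been working from Appendix A. No visits or data are added. Recruitment should not suffer, because exclusion 24 already removes patients expected to need these drugs in that period.
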